### 2.2.3 Safety Population

The safety population includes all subjects who were administered the investigational product, and will be analyzed according to as-treated principle. All safety data will be summarized descriptively based on the safety population.

## 2.3 Study Subjects

### 2.3.1 Subject Disposition

The number of subjects screened will be shown in total and by study center.

The number of subjects in each study population (i.e. ITT, PP, and Safety) will be summarized by study center and in total (by treatment group and overall).

The disposition of subjects will be presented by treatment group, and in total, including numbers of subjects who were:

- Randomized,
- Completed,
- Withdrawn (including primary reason for withdrawal).

These numbers will also be presented by study center. The number of completed and withdrawn subjects will also be presented by visit.

### 2.3.2 Protocol Deviations

Subjects with any protocol deviations will be summarized by study center and in total (by treatment group and overall).

Depending on the seriousness of the deviation, a subject might be excluded from the PP population, which shall be documented prior to database lock. Since the PP population will be used for the primary analysis at Month 1 only, the focus will be on major deviations occurring before and on the Month 1 visit which are considered to have a substantial impact on the primary efficacy outcome. Reasons for exclusion from the PP population will be presented by treatment group and overall.

### 2.3.3 Demographic Characteristics

Subject demographic data will be summarized for the ITT population by treatment group and overall. Age and body mass index will be analyzed as continuous variables. Gender, race, ethnicity, Fitzpatrick skin type, childbearing potential, and toxin naïve status will be analyzed as categorical variables.

### 2.3.4 Medical History, Medications, and Procedures

All summaries will be done for the ITT population by treatment group and overall.

Prior and concomitant medications will be coded using the World Health Organization Drug Dictionary (WHODD). Medical history, allergen history (food, environmental, and drug), and prior and concomitant procedures/non-pharmacological treatments will be coded according to MedDRA.

Prior medications/procedures are the medications/procedures with stop dates prior to study treatment. Medications/procedures after the study treatment will be considered concomitant.

The number and percent of subjects reporting medical history, allergen history, cosmetic treatments/procedures, and prior and concomitant procedures/non-pharmacological treatments will be summarized by system organ class (SOC) and Preferred Term (PT).

The number and percent of subjects reporting prior and concomitant medications will be summarized separately, by WHODD Anatomical Therapeutic Chemical (ATC) Class Level 3 (if Level 3 is not available, will use the highest class available) and WHODD generic name.

## 2.4 Efficacy Analysis

### 2.4.1 Datasets Analyzed

All efficacy variables will be analyzed based on the ITT population. A sensitivity analysis of the primary efficacy endpoint will be performed based on the PP population. Summary statistics will be computed for each efficacy endpoint using the Observed Cases (OC) with no imputation for missing

data. Inferential statistical analyses will account for missing data as appropriate (SAP Section 2.4.2 below).

#### 2.4.2 Handling of Missing Data

The primary and secondary efficacy analyses will be performed using the baseline observation carried forward (BOCF), and the analysis of the primary endpoint will be repeated using multiple imputation (MI) for missing values. If deemed necessary, any analyses may be repeated using OC, BOCF, or MI as appropriate.

##### Multiple Imputation

The imputation using MI will assume Missing Completely at Random (MAR). The MI procedure of the SAS® system will be used to generate five sets of data with missing values imputed from observed data. It is expected that the pattern of missing data will be monotonic, with slight deviations being corrected by the Markov Chain Monte Carlo (MCMC) method of the MI procedure. Linear regression will be employed to model the missing ILA and SSA scores, with the following covariates included in the imputation model: treatment and non-missing data from earlier visits than Month 1. The imputed datasets will be analyzed using the methodology described for the primary analysis. The results from the analysis of the multiple imputed datasets will be combined by the MIANALYZE procedure of the SAS® system.

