5 SELECTION AND DISPOSITION OF CLINICAL STUDY POPULATION

5.1 Number of Subjects

Approximately 400 subjects will be enrolled. In each treatment group, 80 subjects will be treated with abobotulinumtoxinA, and 20 subjects will be treated with placebo.

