### 1.1.2 Number of Subjects and Randomization

The study is planned to enroll approximately 400 subjects who will be treated with [REDACTED] abobotulinumtoxinA (approximately 80 subjects/dose) or placebo (up to 80 subjects depending on the number of dose groups that will run in the study).

Initially, eligible subjects will be randomly assigned at baseline to one of the following treatment

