#### 2.4.3 Primary Efficacy Analysis

The Month 1 responder rates of abobotulinumtoxinA will be compared with placebo

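### The multiple-imputation repeat of the primary analysis uses only five imputed data sets and states no seed, which leaves avoidable Monte Carlo error in a sensitivity result

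*SAP*

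**What the plan says.** SAP Section 2.4.2 makes BOCF the main method for the primary and secondary efficacy analyses and adds that "the analysis of the primary endpoint will be repeated using multiple imputation (MI) for missing values". Any analysis may also be rerun with observed cases, BOCF or MI if that is thought necessary, so inference on observed cases is allowed but not promised.

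Under the Multiple Imputation heading, the SAS MI procedure "will be used to generate five sets of data with missing values imputed from observed data". Linear regression imputes the ILA and SSA scores, with these covariates: "treatment and non-missing data from earlier visits than Month 1". For pooling, "The results from the analysis of the multiple imputed datasets will be combined by the MIANALYZE procedure of the SAS® system". The visible text gives no seed, no reason for five and no expected Month 1 missing rate.

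On size, SAP Section 1.1.2 plans "approximately 80 subjects/dose" and a placebo group of "up to 80 subjects depending on the number of dose groups that will run in the study". For the primary comparison, SAP Section 2.4.3 says: "The Month 1 responder rates of abobotulinumtoxinA will be compared with placebo". The test, the assumed rates and the significance level are not visible in the public text.

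**The concern.** BOCF gives the same answer each time it is run. MI does not: with a finite number of imputations, the pooled estimate, its standard error and its p-value all vary with the random seed. With five data sets, the between-imputation variance B is estimated on 4 degrees of freedom, and the pooled estimate carries simulation error of sqrt(B/5).

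The MI repeat exists to show whether the primary conclusion depends on how missing data are handled. Simulation noise in that repeat blurs the comparison for no benefit. If the MI result fell near a significance limit, a different seed could put it on the other side. With no seed fixed in advance, a reader could fairly ask how the reported one was chosen.

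**Working it through.** **Inputs from the documents.** Number of imputations m = 5 (SAP 2.4.2). About 80 subjects per dose and up to 80 on pooled placebo (SAP 1.1.2). Protocol Section 5.1 agrees: "In each treatment group, 80 subjects will be treated with abobotulinumtoxinA, and 20 subjects will be treated with placebo", and with the four active products in Protocol Table 3, 4 × (80 + 20) = 400. Percentages are reported to one decimal place (SAP 2.1.2). No derivation of m = 5 is visible, so there is no planned figure to reproduce.

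**Assumptions, because the figures are not visible.** FMI or Month 1 missingness of 2%, 5%, 10% or 20%; responder rates of 60% v 2% (large effect) or 20% v 8% (borderline effect); a two-sided 0.05 limit.

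**Step 1: analytic size of the seed effect.** Monte Carlo SD of the pooled estimate divided by its standard error = sqrt(FMI/m). Relative efficiency = 1/(1 + FMI/m). For a result centred at z = 2.0 (p = 0.046), the 95% range of p over seeds comes from z ± 1.96 × sqrt(FMI/m). At FMI = 10% and m = 5 this is 2.0 ± 1.96 × 0.141, or z from 1.72 to 2.28, so p from 0.023 to 0.085.

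| FMI | SD/SE, m = 5 | SD/SE, m = 50 | SD/SE, m = 100 | Relative efficiency, m = 5 | p range at z = 2.0, m = 5 | p range at z = 2.0, m = 50 |
|---|---|---|---|---|---|---|
| 2% | 0.06 | 0.020 | 0.014 | 0.996 | 0.034–0.061 | 0.041–0.050 |
| 5% | 0.10 | 0.032 | 0.022 | 0.990 | 0.028–0.071 | 0.039–0.053 |
| 10% | 0.14 | 0.045 | 0.032 | 0.980 | 0.023–0.085 | 0.037–0.056 |
| 20% | 0.20 | 0.063 | 0.045 | 0.962 | 0.017–0.11 | 0.034–0.061 |

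At z = 3.0 with m = 5, p stays below 0.01 throughout, even at FMI 20% (0.0007–0.0091).

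**Step 2: in percentage points.** For 60% v 2% with 80 per arm, SE = sqrt(0.60 × 0.40/80 + 0.02 × 0.98/80) = 5.7 points. Multiplying by sqrt(FMI/5) gives 0.36 points at FMI 2% and 1.14 points at 20%. For 20% v 8%, SE = sqrt(0.20 × 0.80/80 + 0.08 × 0.92/80) = 5.4 points, giving 0.34 to 1.08 points.

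**Step 3: simulation with the planned type of model.** 80 v 80; two scores from 0 to 3; response assumed to be a 2-grade improvement on both; linear-regression imputation on treatment, baseline and one earlier visit; imputed scores rounded to the scale; Rubin's rules with a t reference. There were 12 data sets per scenario, with 100 seeds at m = 5 and 30 seeds at m = 50.

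| Missing per arm | SD over seeds, 60% v 2%: m = 5 / m = 50 (points) | SD over seeds, 20% v 8%: m = 5 / m = 50 (points) | p range, 20% v 8%, data set nearest p = 0.05: m = 5 | Same data set selection, m = 50 |
|---|---|---|---|---|
| 2% | 0.34 / 0.11 | 0.32 / 0.10 | 0.040–0.058 | 0.045–0.051 |
| 5% | 0.53 / 0.17 | 0.48 / 0.15 | 0.037–0.061 | 0.044–0.051 |
| 10% | 0.74 / 0.24 | 0.59 / 0.19 | 0.020–0.052 | 0.027–0.036 |
| 20% | 1.02 / 0.35 | 0.96 / 0.29 | 0.010–0.061 | 0.022–0.046 |

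For 60% v 2% with m = 5, the upper 97.5% point of p over seeds was at most 2e-7 in every data set. The m = 50 p ranges rest on 30 seeds and are approximate.

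**The case against.** The strongest reply is that little depends on this. The primary result uses BOCF, which has no random element. The study is a phase 2 dose-ranging trial, and no rule is visible that ties a decision to the MI p-value. Relative efficiency with five imputations is at least 0.96 over the assumed range. The 4 degrees of freedom apply only to B; Rubin's reference degrees of freedom are about (m − 1)/FMI², which is 4/0.10² = 400 at 10% and 4/0.05² = 1,600 at 5%. Earlier visits that predict Month 1 bring FMI below the missing rate. SAP 2.1.2 also allows further supportive analyses without an amendment, so a rerun with more imputations is already open to the sponsor.

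All of this stands, and it limits the point to a minor one. It does not justify five. A rerun chosen after the results are known is weaker than a number and seed fixed beforehand, and the precision costs almost nothing.

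A reader might infer three stronger things that the documents do not support:

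- **That MI is the only check on BOCF.** SAP 2.4.2 permits observed-case inference, SAP 2.4.1 plans observed-case summaries, and a per-protocol sensitivity analysis is described, although that varies the population rather than the imputation. MI is only the one missing-data alternative that is committed to.
- **That the MI result will visibly depend on the seed whatever happens.** That needs material Month 1 missingness and, for the p-value to matter, a borderline result. Neither can be seen in the public text.
- **That a seed-dependent check cannot confirm or contradict the primary result.** Noise of 6% to 20% of a standard error does not prevent a comparison of two estimates.

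**Conclusion.** The point holds as a free improvement of low severity. Five imputations without a visible seed leave Monte Carlo error of about 6% to 20% of the standard error for an assumed 2% to 20% missing information, or roughly 0.3 to 1.0 percentage points in the simulated difference. That shows at one decimal place. In the assumed borderline case, the data set nearest p = 0.05 could land on either side of that limit at every missing rate tried. With a large effect only digits of no consequence change, and the BOCF primary result is unaffected in every case.

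The sizes rest on assumed missingness, responder rates, response definition and significance limit. The formula sqrt(FMI/m) needs only the FMI.

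**What to change.** In SAP Section 2.4.2, replace five with at least 50, preferably 100, imputed data sets, and state the seed for the MI procedure. Going from 5 to 50 cuts the Monte Carlo SD by a factor of sqrt(10), about 3.2; going to 100 cuts it by sqrt(20), about 4.5. A result that sits almost exactly on a limit can still cross it with 50, so the seed should be stated as well as the number raised. The cost is a small edit to the SAP and seconds of computing time for about 400 subjects. Nothing changes in data collection, sample size or the primary analysis.

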### 1.2.1 Primary Efficacy Objective

The primary efficacy objective is to evaluate a single dose of [REDACTED] abobotulinumtoxinA, respectively, compared to placebo in the treatment of moderate to severe glabellar lines using the Investigator Live Assessment (ILA) [REDACTED] Photographic Scale and the Subject Self-Assessment (SSA) Static [REDACTED] Categorical Scale at maximum frown at Month 1, concurrently.

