## 1.4 Efficacy Endpoints

### 1.4.1 Primary Efficacy Endpoint

The [REDACTED] responder rate will be evaluated using the ILA [REDACTED] Photographic Scale and the SSA Static 4-Point Categorical Scale of Glabellar Line Severity at maximum frown at Month 1. [REDACTED]

[REDACTED] improvement from baseline

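### The multiple-imputation model for the Month 1 ILA and SSA scores leaves out the link between the two scales, although the endpoint uses both together

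*SAP*

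**What the plan says.** SAP 2.4.2 makes BOCF the primary method and repeats the primary endpoint analysis with MI. For that repeat, "Linear regression will be employed to model the missing ILA and SSA scores", with covariates "treatment and non-missing data from earlier visits than Month 1". Gaps that break the monotone pattern are handled separately, "with slight deviations being corrected by the Markov Chain Monte Carlo (MCMC) method of the MI procedure". Then "The imputed datasets will be analyzed using the methodology described for the primary analysis", and according to 2.4.3 "The Month 1 responder rates of abobotulinumtoxinA will be compared with placebo".

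The endpoint combines two instruments. SAP 1.2.1 evaluates the ILA photographic scale and the SSA "Categorical Scale at maximum frown at Month 1, concurrently". SAP 1.4.1 names the "SSA Static 4-Point Categorical Scale of Glabellar Line Severity at maximum frown at Month 1". The responder rule in 1.4.1 is partly redacted; the surviving words include "improvement from baseline". The number of ILA grades is also redacted. The imputation paragraph itself shows no redaction.

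**The concern.** The covariate list stops before Month 1. A programmer who follows it will impute SSA without the Month 1 ILA score, and ILA without the Month 1 SSA score. Two things follow.

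- When both scores are missing, they are drawn as if independent given treatment and earlier visits.
- When only one is missing, the observed one, likely a strong predictor of the other, goes unused.

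If a responder must pass on both scales, both effects distort the joint rate. What is at stake is the value of the check: MI is the only firmly planned inferential alternative to BOCF. If it under-counts active responders for a technical reason, agreement with BOCF is less reassuring than it looks.

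**Working it through.** The plan states no figure to reproduce here. The responder rule, the ILA length and the expected Month 1 missingness are not visible, so every size below rests on assumptions.

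**Step 1: direction.** Let X be the listed covariates, and let R1 and R2 indicate a pass on ILA and SSA. Then P(both) = E[P(R1|X) P(R2|X)] + E[cov(R1, R2 | X)]. Drawing the scores independently given X drops the second term. Two ratings of the same lines at the same visit should be positively correlated, so the joint rate falls.

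**Step 2: size in the active arm.** Simulation with 400,000 draws per setting: grades 0-3 on both scales, baseline 2 or 3, linear regression on baseline and one earlier visit. Entries are responder rates among imputed subjects; the correlation is the assumed latent residual correlation between ILA and SSA.

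| Rule, both scales | Correlation | True | Rounded, no link | Rounded, with link | Loss from no link (points) | Unrounded, no link |
|---|---|---|---|---|---|---|
| Grade 1 or less | 0.3 | 0.708 | 0.669 | 0.690 | 2.1 | 0.356 |
| Grade 1 or less | 0.6 | 0.736 | 0.670 | 0.713 | 4.3 | 0.357 |
| Grade 1 or less | 0.8 | 0.761 | 0.671 | 0.733 | 6.2 | 0.357 |
| At least 2 grades better | 0.3 | 0.443 | 0.392 | 0.419 | 2.7 | 0.188 |
| At least 2 grades better | 0.6 | 0.478 | 0.393 | 0.447 | 5.4 | 0.188 |
| At least 2 grades better | 0.8 | 0.511 | 0.391 | 0.470 | 7.9 | 0.188 |

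The true rate rises with the correlation, while the no-link column stays at about 0.67 or 0.39. The model cannot see the correlation.

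**Step 3: wider settings.** A second simulation took 45 large-sample cases: 3 effect sizes x 3 rules (the two above and at least 1 grade better) x 5 correlation settings, with 10% missing overall. Leaving Month 1 ILA out of the SSA model lowered the rounded rate in all 45, by 0.5 to 8.2 points among missing active subjects. Further settings reached about 10. Deviation from truth, in points:

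| Imputation model | Same-visit ILA left out | Included |
|---|---|---|
| Linear, rounded and bounded | -11.7 to +2.1 | -4.6 to +2.5 |
| Ordinal | -12.1 to +1.0 | -2.3 to +2.7 |

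Switching to an ordinal model without the link therefore does not cure the problem.

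**Step 4: whole-arm effect.** Effect = missing fraction x loss among missing subjects. The extremes are 0.05 x 0.5 = 0.03 and 0.10 x 10 = 1.0 point. Trial-size runs (80 per arm, 10% missing overall, 7.6 to 8.4% in the active arms) gave a total shift in the active rate of -0.7 to 0.0 for rounded draws with the SAP covariates, against -6.6 to -2.2 for BOCF.

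**Step 5: placebo.** In the Step 2 runs the rounded placebo rate also falls without the link, for example from 0.058 to 0.018 (4.0 points) beside the active loss of 6.2, and from 0.030 to 0.009 (2.1) beside 7.9. With equal missingness in both arms, the difference among missing subjects narrows by 6.2 - 4.0 = 2.2 and 7.9 - 2.1 = 5.8 points, or 0.2 and 0.6 points at 10% missing.

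**Step 6: the conditional part.** If draws were cut without rounding, the under-count among missing active subjects would be 0.443 - 0.188 = 25.5 to 0.761 - 0.357 = 40.4 points in Step 2, and 15.9 to 34.8 in the 45 cases.

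**The case against.** **The text may not mean what it literally says.** A sequential regression can use Month 1 ILA as a predictor of SSA, and the MCMC step is joint. The program may therefore already carry the link. This stands as a possibility. But the covariate list is explicit and unredacted, and MCMC is named only for slight departures from monotone missingness. The MCMC step was not simulated.

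**The effect is small.** This stands. With rounded draws it is below about 1 point of the whole-arm rate, in a repeat of the primary analysis, in a phase 2 study whose sample size is described as exploratory. No conclusion of the trial is shown to change.

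**Two stronger readings are tempting.** A reader might infer that the SAP has no rule for turning continuous draws into grades. The documents do not support that: 2.1.3 (data transformations) is redacted, 1.4.1 partly so, and the visible text of 2.4.3 breaks off after its opening clause. Such a rule could stand in any of them, so the large unrounded figures are conditional. A reader might also infer that MI collapses onto BOCF. It does not: the shifts in Step 4 remain clearly apart, and 2.4.1 also plans observed-case summaries for every efficacy endpoint.

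**Conclusion.** The point holds in a limited form. As written, the imputation model ignores the same-visit link between ILA and SSA. If response requires both scales, the imputed active responder rate is then too low even after rounding: roughly 0.5 to 10 points among missing subjects, and about 1 point or less of the whole arm at 5 to 10% missing.

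This rests on assumed 0-3 grades, a both-scale rule, a positive residual correlation and the assumed missingness. If the two scales were analysed separately, the joint-rate argument would not apply. The active rates are biased downward, which is conservative. For the difference from placebo, that holds at similar missingness in both arms; much more missingness on placebo could offset it, because placebo is under-counted too.

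Whether draws are rounded and bounded is a matter to confirm, not a proven omission. Separately, 2.4.2 spells out MAR as missing completely at random. It should read Missing at Random; this is editorial and changes no result.

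**What to change.** In SAP 2.4.2, state that missing Month 1 ILA and SSA scores will be imputed as ordinal variables by fully conditional specification (FCS), on treatment, baseline and earlier-visit scores, with each model including the other Month 1 score. Responder status is then derived from the imputed grades. An observed Month 1 score is then always used, and non-monotone gaps need no continuous MCMC draws. The ordinal figures in Step 3 are for ILA first and then SSA given ILA; the two-way version was not run.

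If linear regression is kept, add Month 1 ILA to the SSA model, or impute the two jointly. Also confirm, or cross-refer to, a rule that draws are rounded to the nearest grade and bounded to the scale before the responder cut.

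Imputing the composite responder status directly by logistic regression looks simpler, but it should not be used unless it also conditions on any observed Month 1 score. Without that, in one assumed case with SSA missing and an observed ILA score that passes, true response was 84% and the model gave 66%.

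The cost is SAP wording and a few lines of code, with no change to data collection. The downside is sparse placebo cells: under the 2-grade rule, with a placebo rate of about 1%, 46 to 54% of simulated trials had no observed placebo responder. A penalised or collapsed model should therefore be pre-specified.

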6.1.5 Method of Treatment Assignment

Before starting the study, a randomization list stratified by gender will be generated. Female subjects will be further stratified by center; male subjects will not be further stratified by center due to the small number of males expected in the study. When the Investigator has confirmed that all inclusion criteria and no exclusion criteria are met, each subject will be allocated a study product by the Integrated Response Technology (IRT) system.

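### The MI sensitivity analysis, as listed, leaves out scores observed after Month 1 and the randomisation factors for subjects who miss Month 1 but return

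*SAP*

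**What the plan says.** SAP 2.4.2 sets the order of the analyses: "The primary and secondary efficacy analyses will be performed using the baseline observation carried forward (BOCF"), and MI repeats the primary-endpoint analysis only. Under Multiple Imputation the SAP will "generate five sets of data with missing values imputed from observed data". On the model it says "Linear regression will be employed to model the missing ILA and SSA scores", with covariates "treatment and non-missing data from earlier visits than Month 1". On the pattern it says "It is expected that the pattern of missing data will be monotonic". It allows for small departures from this pattern, "with slight deviations being corrected by the Markov Chain Monte Carlo (MCMC) method of the MI procedure". On the assumption it says "The imputation using MI will assume Missing Completely at Random (MAR").

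Three places in the protocol bear on this:

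- Section 7.3.2 refers to a Month 9/early termination visit, so visits after Month 1 exist.
- Section 9.1.3 has every efficacy variable summarised at each visit.
- Section 6.1.5 says "a randomization list stratified by gender will be generated", with further stratification by centre for females only.

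The visit schedule, the secondary endpoints and the detail of the primary test are redacted.

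**The concern.** The SAP allows for slight departures from a monotone pattern. One such departure is a subject who misses Month 1 and then returns. Ratings taken after treatment exist for that subject, but the covariate list stops before Month 1. If the data given to the procedure also stop there, a returning subject looks the same as one who dropped out.

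BOCF treats that subject's Month 1 value as unchanged from baseline whatever was seen later. MI is the only alternative handling of missing values that the SAP commits to, since the other repeats are made only if deemed necessary. A sensitivity analysis that also ignores the later ratings tests less than it could.

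What is at stake is how plausible missing-at-random is for these few subjects. If the chance of missing Month 1 is related to how the subject does later, missingness is at random given the later score but not given the earlier ones alone.

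The randomisation factors are a weaker part of the point. Including them is common practice, but nothing in the documents shows that gender or centre predicts response.

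**Working it through.** The plan states no figure that depends on the imputation model, so there is none to reproduce. The checks below show how many subjects could be affected and what a later visit could add. Every rate and correlation is an assumption except the 400 subjects (Protocol 5.1) and the five imputations (SAP 2.4.2).

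**1. Subjects affected.** Number = 400 × share missing Month 1 × share of those who return.

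- Low: 400 × 0.02 × 0.10 = 0.8, about 1 subject.
- Middle: 400 × 0.05 × 0.25 = 5 subjects.
- High: 400 × 0.10 × 0.50 = 20 subjects.

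**2. Information in a later visit.** Let rE and rL be the correlations of the Month 1 score with an earlier and a later visit, and take the correlation between those two visits as ρ = rE × rL. Then R² with both = (rE² + rL² − 2·rE·rL·ρ)/(1 − ρ²).

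- rE = rL = 0.4: ρ = 0.16, R² = (0.32 − 0.0512)/0.9744 = 0.276, against 0.16 from the earlier visit alone.
- rE = 0.4, rL = 0.8: ρ = 0.32, R² = (0.80 − 0.2048)/0.8976 = 0.663, against 0.16.
- rE = 0.8, rL = 0.4: ρ = 0.32, R² = 0.663, against 0.64.
- rE = rL = 0.8: ρ = 0.64, R² = (1.28 − 0.8192)/0.5904 = 0.780, against 0.64.

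A later visit adds something in each case, but the amount ranges from almost nothing to a great deal. The documents do not say which case applies.

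**3. Effect on the treatment comparison.** This was simulated with 80 against 80 subjects, a latent normal score cut into response or non-response, linear-regression MI with five imputations, Rubin's rules, and 300 replicates per scenario. A model with baseline, an earlier visit and treatment was compared with the same model plus one later visit. Assumed correlations with Month 1 were 0.4 to 0.8 (earlier) and 0.5 to 0.8 (later). Assumed responder rates were 70% against 5%, and 50% against 2%.

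When missingness depends on the later score, the bias in the rate difference, in percentage points, is:

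| Missing at Month 1 | Of these, with later data | Without later visit | With later visit |
|---|---|---|---|
| 2% | all | about +0.3 | 0.1 or less |
| 5% | all | about +0.7 | 0.1 or less |
| 10% | all | about +1.6 | about 0.1 |
| 10% | half | about +1.2 | about +0.6 |
| 10% | none | about +1.4 | about +1.3 |
| 10% (correlations 0.4 earlier, 0.8 later; rates 50% against 2%) | all | +2.0 | 0.0 |

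In the last row the standard error also fell, from 0.0608 to 0.0592.

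When missingness depends on the earlier visit and that visit is in the model, the bias is at most about 0.1 point with or without the later visit. The standard error then falls at most from 0.0593 to 0.0587 (10% missing, all with later data).

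When nobody has later data, adding the visit makes no difference beyond simulation noise.

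The randomisation factors were not simulated, because the documents give no stratum effect.

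**The case against.** The strongest reply is that this refines a sensitivity analysis for very few people. The SAP expects a nearly monotone pattern. Its slight deviations could equally be a missed earlier visit with Month 1 observed, which this point does not touch. The SAP writes of earlier visits in the plural, so scored visits after treatment but before Month 1 may already be in the model. The primary analysis is BOCF and the proposed change leaves it as it is. All of this stands, and it limits the size of the point.

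The MCMC sentence might also be read as bringing later visits into the fill-in step. The text does not exclude that, but the covariate list does not say it, and the list is what a programmer would follow.

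A reader might infer that the plan discards the best predictors of Month 1. The documents do not support that: they give no correlations, the visit schedule is redacted, and a later visit predicts better than an earlier one only if its correlation with Month 1 is higher. The protocol's background describes the licensed effect as temporary, so late visits could be only weakly related to Month 1. The point would be stronger if baseline were the only scored visit before Month 1, but that cannot be seen.

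A reader might also infer that the imputation model conflicts with the analysis model because the strata are missing. The primary test is redacted, so this cannot be established. Adding up to 15 centres to a model with two scales at every visit has a cost of its own.

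**Conclusion.** The point holds as a small improvement to the MI sensitivity analysis. As listed, the model does not use ILA and SSA scores observed after Month 1, and it omits the randomisation factors.

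The benefit is confined to subjects who miss Month 1 and return, perhaps 1 to 20 of 400 on the assumed ranges. Under the assumed inputs, a bias of about 0.3 to 2.0 percentage points is removed when missingness depends on the later score and all affected subjects have later data. With half of them returning, about half of the bias goes. Against assumed responder differences of 48 to 65 points (50 − 2 and 70 − 5), this would not by itself change the conclusion. Under monotone dropout the benefit is nil, and under missingness explained by an earlier visit in the model it is negligible.

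The label in the same paragraph is a separate wording error: it joins the name of one assumption to the abbreviation of another. It should not be read as evidence that the stricter assumption was intended, because a model that conditions on treatment and earlier scores is an ordinary missing-at-random model.

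**What to change.** In the MI sensitivity analysis, impute the ILA and SSA scores jointly over all scheduled visits, before and after Month 1, by MCMC, with treatment and gender as covariates. Add centre, with small centres pooled, if the primary analysis uses it. Then derive Month 1 response from the imputed scores. State that later visits are included, so that the MCMC sentence is no longer ambiguous. If the sponsor prefers the present list, one sentence justifying the omission would do. Correct the label to Missing at Random (MAR).

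The cost is SAP wording and a longer variable list in the same SAS procedure, with a slightly larger imputation model to fit and check. Trial conduct, sample size and the BOCF primary analysis are unchanged.
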